### **10.4.3 Study Patient Description**

#### **10.4.3.1 Disposition of Patients**

The number of enrolled patients will be summarized by country, center, and dose using counts and percentages.

#### **10.4.4 Demographic and Baseline Characteristics**

Baseline characteristics will be described using the patient populations and their accompanying donors. Demographics, medical history, qualifying disorder, and other baseline variables will be summarized as appropriate to the type of data.

#### **10.4.5 Endpoint Analysis**

##### **10.4.5.1 Analysis of Overall Survival**

Overall survival, measured as the period of time from the start of the treatment that the patients are still alive at 1 year and 2 years post-transplant will be assessed and reported.

##### **10.4.5.2 Analysis of Graft Failure**

Secondary graft failure is defined as initial neutrophil engraftment followed by subsequent decline in neutrophil counts < 500 cells/ $\mu$ L, unresponsive to growth factor therapy.

##### **10.4.5.3 Analysis Chronic GVHD**

The time and severity of cGVHD are graded according to NIH Consensus Criteria ([Appendix A](#)).

The initial incidence of severe cGVHD at 6 months will be determined for and will be analyzed by conditioning regimen,  $\alpha\beta$  T cell dose, disease status, and degree of HLA match. The response rates of cGVHD in patients receiving rimiducid treatment will be determined at 6 months and analyzed by the number rimiducid infusion and time to resolution of cGVHD after rimiducid infusion.

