## Appendix B: Management of Chronic GVHD (cGVHD)

Event	Management
cGVHD - Mild	
 
• Consider tissue biopsy to establish diagnosis
 
• Initial treatment with topical or IV steroids, or other systemic treatments (eg, calcineurin inhibitors), per institutional standard of care for mild cGVHD should be instituted. Guidelines for topical corticosteroid treatment include the following (Couriel 2006): 
 
◦ Face, axillae, and groin: lower potency steroids (hydrocortisone 1-2.5%, desonide 0.05%)
 
◦ From the neck down: mid-strength steroids (e.g., triamcinolone 0.1% cream or ointment)
 
 
 
• Systemic corticosteroids when used should be administered as methylprednisolone 2 mg/kg/day IV in a single dose; or a dose equivalent of prednisone or dexamethasone (Martin 1990; see also corticosteroid conversion table C below).
 
• If no response to steroids/systemic therapies occurs within 7 days, or there is a worsening in cGVHD, patients may then receive rimiducid: 
 
◦ Children: 0.4 mg/kg to a maximum of 40 mg IV
 
◦ Adults: 40 mg IV
 
◦ If there is evidence of clinical improvement (e.g. partial response) but not complete resolution after the first dose of rimiducid, then rimiducid may be repeated up to a total of 3 doses beginning 48 hours after the first dose, with each dose separated by 48 hours
 
◦ Daily examination on day 1 and day 2 should be performed after initiating treatment with rimiducid, then weekly for 1 month, every 2 weeks for 100 days, and monthly after 100 days post-rimiducid administration
 
◦ For new or recurrent cGVHD episodes, rimiducid may be considered for repeat administration with the above guidelines if the investigator considered rimiducid to offer clinical benefit with prior episodes.
 
 
 
• If no response to topical steroids or rimiducid, the investigator should consider other medications per institutional guidelines (eg, calcineurin inhibitors, sirolimus, mycophenolate).
 
• Peripheral blood will be used to evaluate BPX-501 cells (CD3+CD19+) at the following times: 
 
◦ Prior to administration of systemic corticosteroid doses (e.g. methylprednisolone), at 4 and 24 hours (<math>\pm</math> 30 minutes) post-systemic corticosteroid doses, and at 7, 14, 21 and 28 days (<math>\pm</math> 24 hours) post-systemic corticosteroid doses
 
◦ When possible, considering patient weight, blood samples will be drawn within 4 hours (<math>\pm</math> 30 minutes) prior to the initiation of rimiducid infusion; 30 mins (<math>\pm</math> 5 minutes) after initiation of the infusion; at 2 hours (< 5 min prior to end of the rimiducid infusion), 4 hours, 6 hours, 8 hours, 12 hours, and 24 hours (<math>\pm</math> 30 minutes) after the initiation of the infusion. Each sample collected out to 24 hours should be split for separate processing. Approximately 0.5 to 1 mL of blood should be processed to plasma and stored at -80 C for later PK analysis of rimiducid. The remaining samples, at least 0.3 mL of blood, should be analyzed locally for prompt CD3+CD19+ T cell analysis. These additional samples (at least 0.3 mL) will be drawn at 48 hours (<math>\pm</math> 30 minutes), then at 7 days (after initiation of infusion of each dose of rimiducid), and at 14 days, 21 days, and 28 days (<math>\pm</math> 24 hours) after the final dose of rimiducid (in
 
 
 

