The resolution of acute GvHD (aGvHD) or chronic GvHD (cGvHD) after administration of rimiducid will be based on the response grading of the GvHD criteria provided in the protocol. The event for this endpoint is any patient who achieved a best overall response (BOR, i.e., either a Complete Response (CR) or Partial Response (PR)) based on aGvHD grading. Only patients experiencing aGVHD who received rimiducid (AP1903) infusion for treatment will be considered for this endpoint. Best overall resolution of aGVHD is defined from the date of AP1903 infusion. The percentage of patients with acute or chronic GvHD, the number of doses of rimiducid, and the best overall response to rimiducid within 7 and 30 days will be presented in listings and summarized. Concomitant medication usage in subjects with acute or chronic GvHD and, further, among those subjects who went on to receive rimiducid, will also be summarized.

Additional analysis and summary statistics will be conducted for resolution of chronic GvHD after administration of rimiducid as well as any case of GvHD (acute or chronic).

(iv) Immune reconstitution as determined by T cell subset counts at day 180

- a. Median and range of CD3 counts at 30, 60, 100 and 180 days
- b. Median and range of CD4 counts at 30, 60, 100 and 180 days
- c. Median and range of CD8 counts at 30, 60, 100 and 180 days

Quantitative assessment of each immune T-cell counts will be performed at various visit time points after transplant as captured in clinical database up to day 180 of follow-up. Analysis and statistical summaries will be performed separately for each T cell subtype assessed. The pattern of each immune reconstitution lab counts will be summarized using graphical summaries and descriptive statistic summary tables including mean (standard deviation), median, and range (minimum, maximum) across the time points assessed. Plots of mean and median cell counts representing measurements over time will be generated to visualize general patterns over time of immune reconstitution.

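### The number of rimiducid infusions depends on response to the first dose, and the 6-month cGVHD response rate has no rule for other systemic therapy

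*Protocol*

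**What the plan says.** **The analysis.** Protocol 10.4.5.3 says that cGVHD response rates in rimiducid-treated patients will be "determined at 6 months and analyzed by the number rimiducid infusion and time to resolution of cGVHD after rimiducid infusion". It does not say whether the 6 months run from transplant or from rimiducid.

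**Who gets more than one dose.** Protocol Appendix B uses the same rule for mild and for moderate-to-severe disease: "If there is evidence of clinical improvement (e.g. partial response) but not complete resolution after the first dose of rimiducid, then rimiducid may be repeated" and this may go "up to a total of 3 doses beginning 48 hours after the first dose, with each dose separated by 48 hours". A new or recurrent episode may be retreated "if the investigator considered rimiducid to offer clinical benefit with prior episodes".

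**What happens to non-responders.** For both severity groups Appendix B says: "If no response to topical steroids or rimiducid, the investigator should consider other medications per institutional guidelines". It gives calcineurin inhibitors, sirolimus and mycophenolate as examples.

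**How response is defined.** Protocol 7.5.1 and Appendix A.2 define complete response (CR) and partial response (PR) from organ findings. Neither sets a condition on other treatment.

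**What the SAP adds.** SAP 6.4.2(iii) presents "the number of doses of rimiducid, and the best overall response to rimiducid within 7 and 30 days". It takes CR or PR as the event in text written for acute GVHD, then extends the analysis to chronic GVHD. Concomitant medication in rimiducid-treated patients is summarised separately and does not enter the response rule. SAP section 2 says that the SAP prevails over the protocols where methods differ.

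**The concern.** Grouping patients by a quantity that is decided after treatment starts, and decided by how they respond, mixes cause and effect. If Appendix B is followed, patients who did not improve after the first dose can be found only in the one-dose group for that episode. A table of response by number of infusions would then show differences between columns even if the second and third doses had no effect at all.

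The 6-month rate raises a separate question. Six months leaves ample time for another drug to be started and to work. As the definitions stand, a patient who failed rimiducid and resolved on the next agent meets the criteria for CR and belongs to the rimiducid-treated set.

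Protocol 7.1 says that the trial will evaluate rimiducid for cGVHD that progresses on, or does not respond to, standard treatment, and evaluating rimiducid for GVHD is the only secondary objective in SAP 3.1. There is no comparator, so the response definition carries all of the interpretation. A dose-number gradient could be misread as support for, or against, repeat dosing.

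**Working it through.** The documents give no target, rate or sample size for this analysis, so there is no planned figure to reproduce. The rules come from the documents; every rate below is an assumption.

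**Step 1. Where patients fall within one episode, under Appendix B**

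- Complete resolution after dose 1: one dose.
- Improved but not resolved: one dose, or two to three, at the investigator's choice.
- Not improved: one dose.

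**Step 2. Response by number of infusions if later doses add nothing**

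Let c = share with CR after dose 1, p = share with PR, n = 1 − c − p, and f = share of PRs re-dosed. Treat those re-dosed as PRs whose response is unchanged.

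- CR+PR, one dose = (c + p(1 − f)) / (c + n + p(1 − f)); two or more doses = 100%.
- CR, one dose = c / (c + n + p(1 − f)); two or more doses = 0%.

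| c | p | f | CR+PR, one dose | CR+PR, two or more | CR, one dose | CR, two or more |
|---|---|---|---|---|---|---|
| 0.1 | 0.2 | 1 | 0.1/0.8 = 12.5% | 100% | 12.5% | 0% |
| 0.1 | 0.2 | 0.5 | 0.2/0.9 = 22% | 100% | 11% | 0% |
| 0.3 | 0.3 | 1 | 0.3/0.7 = 43% | 100% | 43% | 0% |
| 0.3 | 0.3 | 0.5 | 0.45/0.85 = 53% | 100% | 35% | 0% |
| 0.5 | 0.3 | 1 | 0.5/0.7 = 71% | 100% | 71% | 0% |
| 0.5 | 0.3 | 0.5 | 0.65/0.85 = 76% | 100% | 59% | 0% |

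In counts, take 20 treated patients with 6 CR, 6 PR and 8 without response after dose 1, and 4 of the PRs re-dosed. CR+PR is (6 + 2)/16 = 50% with one dose and 4/4 = 100% with more. CR is 6/16 = 37.5% against 0/4.

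The same patients and the same inert later doses therefore give opposite gradients, depending on whether PR is included. Time to resolution plausibly behaves like CR, because those who resolve quickest stop at one dose.

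**Step 3. The 6-month rate if responses on another drug are counted**

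Let r = true rimiducid response and s = share of rimiducid non-responders who respond to another drug. Ignoring loss of response, the observed rate is r + (1 − r)s, and the excess over r is (1 − r)s.

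- r = 0.40, s = 0.2: 0.40 + 0.60 × 0.2 = 52%, an excess of 12 points.
- r = 0.40, s = 0.5: 0.40 + 0.60 × 0.5 = 70%, an excess of 30 points.
- r = 0.40, s = 0.7: 0.40 + 0.60 × 0.7 = 82%, an excess of 42 points.
- r = 0, s = 0.2 to 0.7: 20% to 70%, all of it due to other drugs.
- r = 0.80, s = 0.2 to 0.7: 84% to 94%, an excess of 4 to 14 points.

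If a new systemic agent counts as non-response, the rate returns to r.

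**The case against.** A reader might infer that both planned figures credit rimiducid by construction. The documents do not support that, for these reasons.

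- **Direction.** The gradient favours repeat dosing only for early or best CR+PR. For CR it reverses, as step 2 shows.
- **Timing.** The protocol's rate is taken at 6 months. A re-dosed patient who improved early may have flared by then, so 100% is not guaranteed for that measure.
- **Improvement is not PR.** Appendix B offers PR only as an example of improvement, while 7.5.1 withholds overall PR if any organ progresses. Being re-dosed does not guarantee responder status.
- **Other drugs are optional.** Appendix B asks the investigator to consider them and does not move every non-responder to them. The documents are silent on how later responses are counted, so the 6-month inflation is possible but not certain.
- **The SAP helps in part.** Its 7- and 30-day windows leave less time for another drug to act. It lists number of doses and best response as separate items, and the title of its Table 14.2.4.4 shows no split by dose number.
- **Limited stakes.** Protocol 10.4.2 makes the analysis descriptive, and cGVHD response to rimiducid is not among the objectives in Protocol 5.1 and 5.2.

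All of this stands, and it limits the claim without removing it. Protocol 10.4.5.3 still plans the breakdown by infusion number. Three doses given 48 hours apart fit inside 7 days, so the SAP's windows can mix first and later doses, and 30 days still allows a new agent. The SAP is written for BP-004 and says only that it may draw on BP-404 data, so it is unclear whether it replaces the 6-month analysis.

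**Conclusion.** The point holds in two limited parts.

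**Infusion number.** Under Appendix B it is a consequence of response, so response by number of infusions cannot be read as a dose effect in either direction. This follows from the dosing text alone. The size of the false gradient depends on unknown first-dose rates: under the assumptions above, one-dose CR+PR lies between 12.5% and 76% against 100%, and one-dose CR between 11% and 71% against 0%.

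**Other therapy.** The 6-month rate lacks a counting rule, so responses reached on a later drug can be credited to rimiducid. The size is unknown. The 12 to 42 points rest on an assumed true response of 40%, a 20% to 70% response to other drugs among non-responders, no loss of response, and a decision to count such responses.

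Because the analysis is descriptive and has no comparator, the harm is misreading and not a false test result. The plan should be changed; the trial's primary endpoints are not affected.

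**What to change.** Amend Protocol 10.4.5.3 and SAP 6.4.2(iii).

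1. Replace response by total number of infusions with CR and PR after the first dose in all treated patients, using the assessment on which the re-dosing decision rests. Then report PR-to-CR conversion among those re-dosed. Give the number of infusions as description only.
2. Report the 7-day, 30-day and 6-month rates with the start of a new systemic GVHD agent after rimiducid counted as non-response from that date. Beside each, give the rate regardless of other therapy. State the origin of the 6 months.

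SAP 4.1 confines rimiducid for chronic GVHD to patients with no previous infusion, while Appendix B provides for repeat doses and retreatment. These passages must be reconciled so that the analysis set is clear.

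**Cost.** GVHD treatments are already collected in the EDC, so the second change is wording and programming. The stated response rate may be lower. First-dose response may rest on a short assessment of about 48 hours. The instruction to complete the activity assessment forms stands only in the mild-disease block of Appendix B, so a scored assessment before a second dose may not exist for every patient; the number without one should be reported. Neither change separates rimiducid from the steroids or other systemic therapy already running when it is given. No dosing or treatment rule changes.

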##### **10.4.5.4 Analysis of Time to Disease Relapse**

To assess the incidence of acute leukemia relapse from the day of transplant, a cumulative incidence curve will be computed along with a 95% confidence interval. Death prior to relapse will be considered a competing risk.

##### **10.4.5.5 Transplant-Related Mortality**

The follow-on protocol will determine long-term TRM/Non-Relapse Mortality at 1 year and 2 years, followed by safety evaluations for gene therapy for 15 years.

##### **10.4.5.6 Immune Reconstitution**

Kinetics representing measurements over time within a patient will be generated to visualize general patterns of immune reconstitution. The proportion of iCasp9 positive cells will also be

summarized at each time point. We will also evaluate any indication of differences immune reconstitution across different disease populations.

#### **10.4.6 Safety Analysis**

Safety analysis will investigate the analysis populations over the time period defined as from the infusion date of the respective treatment to study end date.

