#### **9.1.4 Adverse Event Reporting Period**

After informed consent, all adverse events will be reported as per [Table 3](#) which details the guidance for AE reporting after study treatment has initiated.

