**Table 3: Guidance for Adverse Event Reporting**

Event Type	Reporting Period	Additional Requirements
GvHD	All cases of GvHD should be reported regardless of onset date and should	Not applicable

	not be limited to the below AE/SAE reporting period	
AEs (post-IMP)	
 
From the date of BPX-501 infusion until 30 days after administration regardless of causality assessment (including later worsening of events that began during this timeframe).
 
From the date of rimiducid infusion until 30 days after administration regardless of causality assessment.
 
	
 
Report new AEs for up to 15 years if assessed as related to the investigational products BPX-501 and/or rimiducid.
 

SAEs (post-IMP) including Adverse Events of Special Interest*	
 
From the date of BPX-501 infusion until 180 days after administration regardless of causality assessment (including later worsening of events that began during this timeframe).
 
From the date of rimiducid infusion until 30 days after administration regardless of causality assessment.
 
	
 
Report new SAEs for up to 15 years if assessed as related to the investigational products BPX-501 and/or rimiducid.
 
Report diagnosis of any new secondary malignancy regardless of relationship to investigational product for up to 15 years.
 

Pregnancy of patients or partner	
 
12 months after administration of BPX-501 or rimiducid, whichever occurs later.
 
	
 
Report diagnosis of any congenital anomaly in offspring from a study participant or partner for up to 15 years.
 

\* Adverse Events of Special Interest are Grade III-V encephalopathy or neurologic events - these should be reported to the Sponsor expeditiously, irrespective of regulatory seriousness criteria.

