##### **10.4.6.1 Adverse Events (AEs)**

All adverse events recorded during the study will be coded according to the Medical Dictionary for Regulatory Activities (MedDRA) and be graded according to the National Cancer Institute Common Terminology for Adverse Events (NCI CTCAE) v4.03 scale (see [Appendix D](#)).

AEs will be summarized for the following:

- Number (%) of patients with any AE,
- Number (%) of patients with any SAE,
- Number (%) of patients permanently withdrawn from study due to an AE.

All summaries will be presented by treatment group and stratified by type of disorder (e.g. malignant or non-malignant). They will include overall frequency of patients with events as well as frequency of patients with events by primary system organ class and preferred term. A patient will only be counted once within each system organ class and preferred term. For summaries regarding severe or study-drug related AEs, the highest severity or relationship will be considered for each patient per preferred term.

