- 14.2.7 Kaplan-Meier Parameter Estimates of Time to Disease-Free/Chronic-GvHD-Free Survival

- 14.2.8.1-3 Cumulative Incidence Function Parameters of Time to Recovery of Primary Immune Disorders as Determined by CD3 T Cell Count >500 cells/uL, and Normal Levels of IgA and IgM

- 14.2.8.2 Cumulative Incidence Function Parameter Estimates of Time to Recovery of Haemoglobinopathies as Determined by Incidence of RBC Transfusion Independence and Haemoglobin of >8.5 g/dL
- 14.2.8.3-3 Cumulative Incidence Function Parameter Estimates of Time to Recovery of Fanconi Anemia as Determined by RBC > 3,000,000 cells/uL, Neutrophil Count > 1500 cells/uL, and Platelet Count >150,000
- 14.2.8.4 Kaplan-Meier Parameter Estimates of Relapse-Free Survival in Subjects with Leukemia
- 14.2.8.5 Cumulative Incidence of Relapse in Subjects with Acute Leukemia
- 14.2.9 Cumulative Incidence Function Parameter Estimates of Time to Neutrophil Engraftment
- 14.2.10 Cumulative Incidence Function Parameter Estimates of Time to Platelet Engraftment
- 14.2.11 Graft Failures

- 14.2.12.1 Time to Any Grade Infection
- 14.2.12.2 Time to Grade 3 or Higher Infection
- 14.2.13.1 Kaplan-Meier Parameter Estimates of Overall Survival
- 14.2.13.2 Kaplan-Meier Parameter Estimates of Disease-Free Survival in Subjects with Non-Malignant Disease
- 14.2.13.3 Sensitivity Analysis: Kaplan-Meier Parameter Estimates of Disease-Free Survival, by Dosing Window
- 14.2.13.4 Kaplan-Meier Parameter Estimates of Relapse-Free Survival in Subjects with Malignant Disease
- 14.2.13.5 Sensitivity Analysis: Kaplan-Meier Parameter Estimates of Relapse-Free Survival, by Dosing Window in Subjects Dosed at 1×10^6 Cells/kg
- 14.2.13.6 Sensitivity Analysis: Kaplan-Meier Parameter Estimates of Relapse-Free Survival, by Dosing Window in Subjects Dosed at 1×10^6 Cells/kg or Above
- 14.3.1.1 Treatment-Emergent Adverse Events Summary
- 14.3.1.2 Treatment-Emergent Adverse Events Regardless of Relationship to Study Treatment by System Organ Class, Preferred Term, and Dose of BPX-501
- 14.3.1.3 Treatment-Emergent Adverse Events Related to Occurring After AP1903 Administration, by System Organ Class, Preferred Term, and Dose of BPX-501
- 14.3.1.4.1 Treatment-Emergent Adverse Events Regardless of Relationship to Study Treatment, by System Organ Class, Preferred Term, and Maximum Severity
- 14.3.1.4.2 Treatment-Emergent Adverse Events Occurring After AP1903 Administration, by System Organ Class, Preferred Term, and Maximum Severity

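### BP-404 tabulates any AE and any SAE through to study end, although all-cause reporting closes 30 days (AEs) or 180 days (SAEs) after BPX-501

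*Protocol*

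**What the plan says.** **Analysis period.** Protocol 10.4.6 defines one safety window, "from the infusion date of the respective treatment to study end date". Section 9.3 closes the study once 15 years of follow-up after BPX-501 are complete.

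**Tables.** Section 10.4.6.1 lists "Number (%) of patients with any AE" and "Number (%) of patients with any SAE", overall and by system organ class and preferred term. They are not split by time since infusion or by relatedness.

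**Reporting rule.** Section 9.1.4 states: "After informed consent, all adverse events will be reported as per" Table 3. For AEs, Table 3 says "From the date of BPX-501 infusion until 30 days after administration regardless of causality assessment". For SAEs it says "From the date of BPX-501 infusion until 180 days after administration regardless of causality assessment". Both rows add a window for rimiducid: "From the date of rimiducid infusion until 30 days after administration regardless of causality assessment". Outside these windows, new AEs and SAEs are reported to year 15 only if judged related to BPX-501 or rimiducid.

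**Exceptions.** GvHD is reported whenever it starts (Table 3 and 9.1.5). Any new secondary malignancy, and any congenital anomaly in offspring, is reported for 15 years. Worsening of an event that began inside the post-BPX-501 window also counts.

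**Entry.** Section 5.4 admits patients who received BPX-501 in BP-004 and are past Day 180.

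**The concern.** The period over which events are counted is far longer than the period over which all events are requested. From day 31 (AEs) or day 181 (SAEs) after BPX-501, a late infection or neurological event judged unrelated need not be reported under Table 3. The patient stays in the denominator and appears event-free.

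Long-term safety to 15 years is the main secondary endpoint in the synopsis. A reader of a row for any SAE over infusion to study end would take it as all-cause incidence. For most of that time it depends on the investigator's causality judgement in an uncontrolled study, and nothing in 10.4.6 or 10.4.6.1 requires the table to say so.

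**Working it through.** The plan states no figure on this point, so there is none to reproduce.

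**1. Share of follow-up under all-cause reporting after BPX-501** (windows from Table 3, follow-up from 9.3)
- 15 years = 15 × 365.25 ≈ 5,479 days. AEs: 30/5,479 = 0.5%. SAEs: 180/5,479 = 3.3%.
- 2 years = 730.5 days. AEs: 30/730.5 = 4.1%. SAEs: 180/730.5 = 24.6%.

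**2. How much of this can fall inside BP-404.** SAP 4.1 gives BPX-501 at 14 ± 4 days after transplant (Day 10–18), or 21 ± 14 days under some versions (Day 7–35). I take Day 180 in the entry criterion as counted from transplant, in line with SAP 4.4.
- SAE window closes at Day 190–198 (10 + 180 to 18 + 180), or at Day 187–215 (7 + 180 to 35 + 180).
- The most that can overlap with BP-404 is therefore 187 − 180 = 7 days to 215 − 180 = 35 days.
- AE window closes by Day 65 at the latest (35 + 30), before anyone can enter.

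**3. Direction.** Reported events are a subset of all events, so the reported percentage cannot exceed the all-cause percentage. This needs no assumption about rates.

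**4. Illustration of size for SAEs, on assumed inputs.** P0 is the proportion with an SAE by 180 days after BPX-501, h the later all-cause yearly hazard of a first SAE, r the share judged related, and t the years after the window. None of P0, h or r is in the documents.
- All-cause: 1 − (1 − P0)·exp(−h·t)
- Captured: 1 − (1 − P0)·exp(−h·r·t)
- t = 2 − 180/365.25 = 1.507 years, or 15 − 180/365.25 = 14.507 years

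Example at 15 years with P0 = 0.6, h = 0.05, r = 0.1: all-cause 1 − 0.4·exp(−0.725) = 80.6%; captured 1 − 0.4·exp(−0.0725) = 62.8%; shortfall 17.8 points.

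Range over h = 0.02–0.10 and r = 0–0.25:

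| P0 | Shortfall at 2 years (points) | Shortfall at 15 years (points) |
|---|---|---|
| 0% | 2.2–14.0 | 18.2–76.6 |
| 10% | 2.0–12.6 | 16.4–68.9 |
| 30% | 1.6–9.8 | 12.7–53.6 |
| 60% | 0.9–5.6 | 7.3–30.6 |
| 90% | 0.2–1.4 | 1.8–7.7 |

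The shortfall scales with (1 − P0). Patients already counted for an early event protect the top-line row. Rows for single system organ classes or preferred terms have fewer early cases and less protection, although their hazards would also be lower than those used here. The model ignores death as a competing event, the exceptions in Table 3 and the rimiducid windows, so the 15-year figures are at the upper end.

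**The case against.** **The reporting rule may be wider than Table 3.** Section 9.2.4 requires every SAE to be reported within 24 hours, with no time or causality limit. Section 9.1.3 makes the investigator responsible for recording and reporting all SAEs. Section 9.2.3 asks for all CNS events with apparent encephalitis of Grade 3 or higher, again without a limit. Table 1 marks adverse events at every visit to year 15. This stands in part. Section 9.1.4 sends adverse event reporting to Table 3, and 9.1.3 itself defers to protocol instructions, so Table 3 is the better reading. But the passages are not reconciled. If unlimited SAE reporting is intended, the SAE half of the point falls away and the AE half remains.

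**The any-AE rows may mean any recorded AE.** Section 10.4.6.1 does speak of events recorded during the study. That makes the row literally true, but a reader still cannot tell that late unrelated events were not requested.

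**The follow-up targets gene therapy safety.** Section 9.3 says so, and related events, GvHD and secondary malignancy are requested throughout. This stands: the understatement concerns all-cause incidence only. Safety output is also descriptive (Protocol 10.4.2, SAP 6.5), so no test is affected.

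**The SAP titles are not BP-404 titles.** A reader might combine the BP-404 window with SAP 7.1.1, which lists "Treatment-Emergent Adverse Events Regardless of Relationship to Study Treatment by System Organ Class, Preferred Term, and Dose of BPX-501", and infer that a 15-year all-cause table is planned. The documents do not support that. The SAP is based on BP-004 (SAP section 2), and its final analysis follows at least 2 years of follow-up of the last UK subject (SAP 5.2). The BP-004 reporting periods are not among the documents. The SAP matters here only because its analyses beyond Day 180 may draw on BP-404 data and its treatment-emergent definition (6.5) has no end date.

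**Conclusion.** The mismatch between 10.4.6/10.4.6.1 and Table 3 is real, and nothing in either document resolves it. If the stated rules are followed, the any-AE and any-SAE percentages understate all-cause incidence over BP-404 follow-up. This rests on Table 3 governing reporting and on Day 180 being counted from transplant.

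The size cannot be derived from the documents. It could be a point or two in a top-line row where most patients have an early SAE, and much more where early events are few.

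A reader might start every patient event-free at Day 180 and assume 5–10 SAEs per 100 patient-years for 1.5 years with 10–20% called related. That sets 7–14% of patients with an SAE (1 − exp(−0.05 × 1.5) to 1 − exp(−0.10 × 1.5)) against 0.7–3% captured. It is not the error in the 10.4.6.1 rows, which count from infusion and so include earlier events. On the same assumptions the shortfall is 5.7–12.4 points if no one had an earlier SAE, 2.3–5.0 if 60% had, and 0.6–1.2 if 90% had.

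This should be corrected before the long-term safety tables are produced. It does not affect the survival endpoints.

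**What to change.** 1. In Protocol 10.4.6 and 10.4.6.1, restrict all-cause tables to onset within the Table 3 windows: 30 days (AEs) or 180 days (SAEs) after BPX-501, and 30 days after each rimiducid dose. State that the post-BPX-501 windows draw on BP-004 data, because BP-404 itself observes none of the AE window and at most about 35 days of the SAE window.
2. Tabulate related AEs and SAEs, GvHD and secondary malignancy separately over long-term follow-up, with the reporting rule in each title. Use person-time rates, or cumulative incidence with death as a competing event. The number still under follow-up is not a valid denominator for cumulative counts, because it drops patients who had an event and then died or left.
3. Apply the same split to SAP outputs only where they include BP-404 data beyond Day 180.
4. Reconcile 9.1.3, 9.2.3 and 9.2.4 with Table 3, so that one rule states which SAEs and CNS events are reported, and for how long.

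Cost: a protocol text edit, changes to table shells and a few more tables. Steps 1 to 3 need no new data. Step 4 would add data collection beyond Table 3 only if the wider SAE rule is the one intended.
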